5. STATISTICAL ANALYSES

5.1. General Considerations

All data collected in this study will be presented separately by disease cohort using summary tables, figures, and data listings. All analyses will be performed using Statistical Analysis Software® (SAS) release, V 9.4 or higher (SAS Institute Inc., Cary, NC, USA) or other validated statistical software.

All efficacy and safety analyses will be summarized separately for the Initial Evaluation Period, Extension Period, and Post-treatment Follow-up Period. Limited data will be collected during the Post-treatment Follow-up Period and will be summarized descriptively, as appropriate.

The analyses for participants in the LN cohort and participants with IgAN cohort will be conducted and reported separately.

Continuous variables will be summarized using descriptive statistics, including number of observations and mean, SD, median, minimum, and maximum values. Categorical variables will be summarized by frequency counts and percentage of patients.

Unless otherwise specified, data collected at an unscheduled visit will be included in by-patient listings but not in the summary tabulations. However, unscheduled study visits will be used in the calculation of baseline values.

Summaries of study and participant characteristics (eg, demographics and baseline characteristics, medical history, protocol deviations) are described in Section [6.2](#).

5.1.1. Data Presentation for the Initial Evaluation Period

Data summaries for the Initial Evaluation Period will be presented by randomized treatment group (ie, “Ravulizumab” and “Placebo”) and overall, if applicable. For the IgAN cohort, summaries will be presented by treatment sequence (ie, “Ravulizumab to Ravulizumab” and “Placebo to Ravulizumab”). Baseline is defined as the last value prior to the start of study intervention. All assessments for Week 26 will be performed prior to dosing. Dosing on Week 26 will be considered the start of the Extension Period.

5.1.2. Data Presentation for the Extension Period

Data summaries for the Extension Period will be presented by randomized treatment group and overall, if applicable. For the IgAN cohort, summaries will be presented by treatment sequence (ie, “Ravulizumab to Ravulizumab” and “Placebo to Ravulizumab”). In addition, baseline for the IgAN cohort will be defined as the last value prior to their initial exposure to ravulizumab.

5.1.3. Data Presentation for the Post-treatment Follow-up Period

Data summaries for the Post-treatment Follow-up Period will be presented by randomized treatment group and overall, if applicable. For the IgAN cohort, summaries will be presented by treatment sequence (ie, “Ravulizumab to Ravulizumab” and “Placebo to Ravulizumab”).

5.1.4. Handling of Dropouts or Missing Data

No imputation will be performed for missing baseline values.

To derive duration of disease, partial date of diagnosis will be imputed. If Day is missing, then impute to the 1st. If Day and Month are missing, then impute to Jan 1st. Concomitant medication start date and AE start date will follow the same imputation rule to derive the study phase.

Missing data for QoL instruments will be handled as specified in the instructions for each instrument in Section [6.3](#).

In addition, the following intercurrent events may occur during the study:

1. Receipt of additional standard-of-care therapy (LN cohort only)
2. Treatment discontinuation

For the primary efficacy endpoint, only data up to the point of additional standard-of-care therapy will be included as observed. For participants in the LN cohort who receive additional standard-of-care therapy, the proteinuria value from the 24-hour urine collection performed at the time of renal flare or severe extrarenal SLE flare will be carried forward to subsequent visits. Data occurring on or after treatment discontinuation will be assumed missing-at-random (MAR) and imputed using multiple imputation as described in Section [5.3.2](#). For participants who experience multiple intercurrent events, data will be handled according to the first intercurrent event.

Additional sensitivity analyses are specified in Section [5.3.3](#).

For secondary responder endpoints, participants who receive additional standard-of-care therapy or discontinue treatment are assigned as nonresponders regardless of whether there is any response observed after these protocol-defined intercurrent events. For missing postbaseline data not due to intercurrent events, no imputation will be performed.

A summary of the primary and secondary estimands for this study is provided in [Table 1](#).

Table 1: Estimands

Estimand	Treatment	Population	Variable	Handling of IE	Summary Measure
Primary	Ravulizumab or placebo	Full Analysis Set	Percentage change from baseline to Week 26 in proteinuria (both cohorts)	Data on or after receipt of additional standard-of-care therapy (LN cohort only) will be imputed using the value collected at the time of renal flare or severe extrarenal SLE flare Data on or after treatment discontinuation will be imputed using multiple imputation	Difference in mean of the variable between treatment groups
Secondary (key continuous endpoints)	Ravulizumab or placebo	Full Analysis Set	Percentage change from baseline to Week 50 in proteinuria (both cohorts) Change from baseline in eGFR at Week 26 and Week 50 (both cohorts)	Data on or after receipt of additional standard-of-care therapy (LN cohort only) will be imputed using the value collected at the time of renal flare or severe extrarenal SLE flare (or suboptimal after Week 26, if applicable) Data on or after treatment discontinuation will be assumed missing and handled in the MMRM as MAR	Mean of the variable in each treatment group

Table 1: Estimands

Estimand	Treatment	Population	Variable	Handling of IE	Summary Measure
Secondary (key binary endpoints)	Ravulizumab or placebo	Full Analysis Set	
Percentage of participants with > 30% and > 50% reduction in proteinuria at Week 26 and Week 50 compared to baseline (both cohorts)
 
Percentage of participants meeting the criteria for CRR at Week 26 and Week 50 (LN cohort only)
 
Percentage of participants meeting the criteria for PRR at Week 26 and Week 50 (LN cohort only)
 
Percentage of participants meeting the criteria for Partial Remission at Week 26 and Week 50 (IgAN cohort only)
	
Participants who receive additional standard-of-care therapy (LN cohort only) or discontinue treatment are assigned as nonresponders
	Proportion of the variable in each treatment group

Abbreviations: CRR = complete renal response; eGFR = estimated glomerular filtration rate; IE = intercurrent events; LN = lupus nephritis; MAR = missing-at-random; MMRM = mixed effect model for repeated measures; PK = pharmacokinetics; PRR = partial renal response

The secondary estimands for all other secondary endpoints are similar to above except the intercurrent events will be ignored and all data occurring on or after the intercurrent event will be analyzed as observed.

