5.6. Safety Analyses

All safety analyses will be performed on the Safety Set and will be based on the actual treatment received. All safety data will be provided in patient listings by treatment group.

AEs will be coded in MedDRA V 23.0 or higher and presented by MedDRA system organ class (SOC) and preferred term (PT).

No formal hypothesis is planned. Safety data will be presented separately for the Initial Evaluation Period, Extension Period, and Post-treatment Follow-up Period.

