5.6.2. Adverse Events

The following definitions will be used for AEs:

- **Pretreatment AE:** Any AE that starts after providing informed consent, but before the first infusion of study intervention (ravulizumab or placebo).
- **Treatment-emergent adverse event (TEAE):** Any AE that starts between the start of the first infusion of study intervention and up to 56 days after the last infusion of study intervention.
- **Treatment-emergent SAE (TESAE):** A TEAE that is serious.
- **Post-treatment AEs:** Any AE that starts 56 days or later after the last infusion of study intervention.

All AEs will be coded using MedDRA V 23 or higher and will be summarized by SOC and PT overall, by severity, and by relationship to treatment. Participants having multiple AEs within a category (eg, overall, SOC, PT) will be counted once in that category. For severity/relationship tables, the participant's highest grade/most related event within a category will be counted.

TEAEs and SAEs will be summarized descriptively by treatment group. Percentages will be based on the number of treated participants in the Safety Set within a treatment group. Tables will be sorted by alphabetic order of SOC and by descending frequency of PT within an SOC.

Pretreatment and post-treatment AEs will be provided in by-participant listings and will not be included in summary tables.

In addition, AEs that occur after the receipt of additional standard-of-care therapy will be provided in a separate listing.

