6.1.7. AEs

The analysis of AEs is described in detail in Section [5.6.2](#).

Treatment-emergent AEs (TEAEs) are events with start dates and start times on or after the date and time of the first dose of study intervention and up to 56 days after the last dose of study intervention. If the start date of an AE is partially or completely missing and the end (stop) date and time of the AE does not indicate that it occurred prior to first dose or 56 days after the last dose, then the determination of treatment-emergent status will be based on the following:

- If the start year is after the year of the first dose of study intervention and before the year of the last dose of study intervention, then the AE is treatment-emergent; else
- If the start year is the same as the year of the first dose of study intervention and
 - the start month is missing, then the AE is treatment-emergent; else if
 - the start month is present and is the same or after the month of the first dose of study intervention and is the same or before the last dose of study intervention, then the AE is treatment-emergent; else,
- If the start date is completely missing, then the AE is treatment-emergent.

All other AEs are considered pretreatment AEs if the start date is prior to the first dose of study intervention or post-treatment AEs if the start date is 56 days or later after the last dose of study intervention.

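### The SAP back-dates partial AE and medication start dates to derive study phase, which conflicts with its treatment-emergent rules at first dose and misplaces IgAN placebo-arm events at the Week 26 switch

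*SAP*

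**What the plan says.** SAP 5.1.4 gives a rule for partial dates of diagnosis, needed for disease duration: "If Day is missing, then impute to the 1st. If Day and Month are missing, then impute to Jan 1st". The next sentence reuses it: "Concomitant medication start date and AE start date will follow the same imputation rule to derive the study phase". That section sets no lower bound at any dose date and does not look at the stop date.

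Phase then governs the display. SAP 5.6 states: "Safety data will be presented separately for the Initial Evaluation Period, Extension Period, and Post-treatment Follow-up Period". SAP 5.1.1 makes the Week 26 dose the start of the Extension Period. SAP 5.6.2 defines a pretreatment AE as one that begins between consent and the first infusion, and adds: "Pretreatment and post-treatment AEs will be provided in by-participant listings and will not be included in summary tables".

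Two appendix sections treat the same partial dates differently, unless the stop date settles the matter:

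- SAP 6.1.7, for an AE dated to the first-dose year, reads "the start month is missing, then the AE is treatment-emergent; else if". It gives the same status when "the start month is present and is the same or after the month of the first dose of study intervention", provided the month is not after the last dose. It also states: "If the start date is completely missing, then the AE is treatment-emergent".
- SAP 6.1.10 uses parallel wording that makes the matching medication concomitant.

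In the IgAN cohort, placebo participants receive a ravulizumab loading dose at Week 26 (SAP 1.2). LN participants keep their randomized drug throughout.

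**The concern.** Taking the earliest possible day is harmless for a diagnosis that lies well before the study. It is a poor way to decide on which side of a dose an event began, because every error goes to the earlier phase.

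At the first dose, one AE can carry a treatment-emergent flag and a pre-dose phase. A programmer who builds a treatment-emergent table by period has no instruction on whether to count it.

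At Week 26 the phase boundary is also the exposure boundary for the IgAN placebo arm. An event from the first weeks on ravulizumab can be added to the placebo-controlled period and taken out of the ravulizumab period.

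**Working it through.** The plan gives no figure to reproduce, so the rules were applied to calendar dates.

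**Inputs.** The Extension starts at the Day 183 dose (Protocol Table 4; SAP 5.1.1) and runs to the Week 50 visit, Day 351. The Initial Evaluation Period is therefore Days 1 to 182 (182 days) and the Extension Days 183 to 351 (169 days). Allocation is 40 ravulizumab and 20 placebo per cohort. First-dose dates and AE onsets are assumed uniform over the calendar; this is an assumption, not a figure from the documents.

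**Example.** Take a first dose on 10 March 2023. Day 183 is 182 days later, 8 September 2023.

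| True AE start, day not recorded | Phase under 5.1.4 | Status under 6.1.7 |
|---|---|---|
| 20 March 2023 | 1 March: pre-dose | Treatment-emergent |
| 20 September 2023, IgAN placebo arm | 1 September: Initial Evaluation (placebo) | Treatment-emergent; silent on Week 26 |

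SAP 6.1.7 cannot correct the second row. Its partial-date bullets are tied only to the first and last dose, for example "If the start year is after the year of the first dose of study intervention and before the year of the last dose".

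**Day missing, within the first-dose month.** In a 30-day month with dose day and AE day both uniform, the AE is set to pre-dose unless the dose is on the 1st: 29/30 of cases. That is the share assigned pre-dose, not the share assigned wrongly. The wrong ones began on or after the dose: 465 of the 900 day pairs, less the 30 with the dose on the 1st, so 435/900 = 48%.

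**Day missing, share of a whole phase.** In a month of L days with the boundary dose on day u, the back-dated days are L − u + 1 for u ≥ 2 and none for u = 1. The mean is (L − 1)/2. Over a 365-day year this is (7 × 465 + 4 × 435 + 378)/365 = 5,373/365 = 14.7 days.

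- Initial Evaluation to pre-dose: 14.7/182 = 8.1%.
- Extension to Initial Evaluation: 14.7/169 = 8.7%.

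**Day and month missing.** The AE stays in its phase only if a 1 January falls between the start of that phase and the AE.

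- Initial Evaluation: mean study day 91.5; 91.5/365.25 = 25.1% stay and 74.9% become pre-dose.
- Extension: mean day within the phase 85; 85/365.25 = 23.3% stay and 76.7% leave. Mean study day is 267; 267/365.25 = 73.1% have a 1 January on or after Day 1. So 73.1 − 23.3 = 49.8% go to Initial Evaluation and 26.9% to pre-dose.

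A day-by-day enumeration, with first-dose dates every third day over four years, gives the same shares: 8.1% and 8.7% with the day missing; 74.9% and 76.7% with the month missing (the latter 49.9% to Initial Evaluation and 26.8% to pre-dose).

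**Follow-up.** The same enumeration moves 5.9% of day-missing and 44.5% of month-missing Follow-up AEs back into the Extension.

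All percentages are shares of AEs with partial dates.

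**The case against.** The case for leaving this alone has weight. The safety tables are descriptive and carry no hypothesis test. Treatment-emergent status has its own detailed rule in SAP 6.1.7, so loss of events from the summary tables is not established; what exists is an unresolved conflict. The drug changes at the boundary in one arm of one cohort only. Protocol 8.5.2 requires start and end dates for medications, so partial dates may be few. All of this stands, and it limits the size of the point. It does not remove the conflict, and 6.1.7 says nothing about Week 26.

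A reader might infer more than the documents support:

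- *That the rule always moves events away from ravulizumab.* It does not. The first-dose shift affects both arms by the same rule. LN participants and the IgAN ravulizumab arm have the same drug on both sides of Week 26. Follow-up events move toward the treatment period.
- *That 29 of 30 first-dose-month AEs are misplaced.* AEs are collected from consent, and Screening lasts up to 6 weeks, so many of these are truly pre-dose. On uniform timing about 48% are wrong.
- *That infections are hit hardest.* Nothing shows that they have more partial dates. SAEs are reported within 24 hours, and meningococcal events have their own table, listing and medical review (SAP 5.6.2.5 and 6.1.8).
- *That LN additional-therapy starts are moved.* SAP 5.4.11 takes these from the Rescue Therapy eCRF, and 5.1.4 does not say that it governs them.

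**Conclusion.** The point holds in two parts.

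First, SAP 5.1.4 contradicts 6.1.7 and 6.1.10 for partial dates compatible with the first dose. It does so in both arms of both cohorts, with no stated precedence. This rests on the text alone.

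Second, for about 20 IgAN participants switching from placebo, 5.1.4 as written places some ravulizumab-period AEs in the placebo period or earlier. The 8.7% and 76.7% shares of Extension AEs depend on uniform timing and on complete follow-up to Week 50. They apply only to AEs with partial dates, a number the documents do not give. If few dates are partial, the absolute effect is small. It bears on the by-period safety displays, not on the primary endpoint, and is worth correcting before those tables are programmed.

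**What to change.** Amend SAP 5.1.4 as follows.

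1. Limit the 1st / 1 January rule, as it stands, to the date of diagnosis.
2. For AE and medication phase, where the known date parts allow a start on or after the first dose and 6.1.7 or 6.1.10 makes the record treatment-emergent or concomitant, the imputed start may not precede the first-dose date. A medication known to have begun in an earlier month keeps that month.
3. In both arms of the IgAN cohort, where the Week 26 dose date lies within the span that the known parts allow and the stop date does not precede that dose, set the start to the Week 26 dose date. Where both dose dates are compatible, the later applies.
4. Otherwise use the 1st of the month, or 1 January if the month is missing, subject to item 2.
5. State that phase under 5.1.4 follows 6.1.7 and 6.1.10.

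The cost is a few lines of SAP text and derivation code, with no new data. The downside is that some true pre-dose or placebo-period events will be counted in the later phase. At the IgAN switch that is the conservative direction for ravulizumab safety. It also removes a few partially dated events from the Initial Evaluation tables of both IgAN arms, so a count of AEs whose start was imputed, by arm and period, should accompany the tables.

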5.2. Study Participants

A summary of disposition will be presented by treatment group and overall and will include the number and percentage of participants screened, screen failed, randomized, and treated. The number and percentage of participants who completed the study or discontinued from the study (along with the primary reason for discontinuation) will be presented. Discontinuation status will be presented overall as well as separately for discontinuations impacted by COVID-19. Disposition will be presented separately for the Initial Evaluation Period, Extension Period, and Post-treatment Follow-up Period.

The number and percentage of participants in each defined analysis set will also be presented.

A summary of enrolled participants by region will be presented by treatment group and overall.

Participants who are randomized but did not satisfy the inclusion/exclusion criteria will be presented by treatment group and overall for each criterion not satisfied.

By-participant data listings for disposition and analysis populations will be provided, as well as a listing of participants who did not satisfy the inclusion/exclusion criteria.

5.3. Primary Endpoint Analysis

The primary efficacy endpoint analysis will be based on the FAS.

The analyses for participants in the LN cohort and participants in the IgAN cohort will be conducted and reported separately. Participants in each disease-specific cohort will be analyzed as randomized, regardless of actual treatment received.

The randomization stratification factor will be based on strata verified by central laboratory and allowed concomitant therapy data from electronic case report forms (eCRFs). Sensitivity analysis may be performed using strata as randomized in IXRS (Interactive Voice/Web Response System).

5.3.1. Percentage Change from Baseline in Proteinuria

The primary endpoint for the study is percentage change from baseline to Week 26 in proteinuria based on 24-hour urine collection(s) at each timepoint.

Proteinuria will be summarized by absolute urine protein in g/day as well as by UPCR in g/g for each disease-specific cohort.

For participants in the LN cohort, the primary endpoint will be based on UPCR in g/g derived from a single 24-hour urine collection at Screening and the mean of 2 separate 24-hour urine collections within 2 weeks of the Week 26 visit.

For participants in the IgAN cohort, the primary endpoint will be based on absolute urine protein in g/day derived from the mean of 2 valid 24-hour urine collections during the Screening Period and within 2 weeks of the Week 26 visit.

5.3.2. Main Analytical Approach

The primary analysis of the primary efficacy endpoint (percentage change from baseline in proteinuria at Week 26) will be conducted for each disease-specific cohort after all participants have completed the protocol-required assessments in the Initial Evaluation Period.

For the primary efficacy endpoint, when two 24-hour urine collections are required and only 1 collection is available at the visit, then this value will be used for analysis. When more than 2 collections are available at the visit, only 2 valid collections recorded in the eCRF will be used for analysis.

To reduce skewness, the natural logarithm will be used to transform proteinuria values before analysis. An analysis of covariance (ANCOVA) will be used for the primary efficacy endpoint to compare reductions in proteinuria between the ravulizumab and placebo treatment groups. The ANCOVA model will include change from baseline in log-transformed proteinuria as the response variable and will adjust for baseline log proteinuria and the randomization stratification factor. The treatment effect will be evaluated using the least squares mean difference between treatment groups. The point estimate and 2-sided 90% confidence interval (CI) for the mean difference of log-transformed proteinuria will be back transformed (via exponentiation) to obtain the GMR and corresponding 2-sided 90% CI. The values will then be expressed as percentage change in adjusted geometric mean of proteinuria at Week 26 relative to baseline.

Data collected on or after receipt of additional standard-of-care therapy (for LN cohort) will be imputed using the proteinuria value from the 24-hour urine collection performed at the time of renal flare or extrarenal SLE flare. Data collected on or after treatment discontinuation will be assumed MAR and imputed using multiple imputation.

